5.5.6 Rescue medication

Guidance on handling renal dysfunction, hyperkalemia, and hypotension are provided to investigators in [Appendix 3](#), [Appendix 4](#), and [Appendix 5](#), respectively.

Use of rescue medication must be recorded on the Concomitant Medications eCRF.

5.5.7 Concomitant medication

The investigator should instruct the patient to notify the study site about any new medications he/she takes after the patient was enrolled into the study. All medications, procedures and significant non-drug therapies (including physical therapy and blood transfusions) administered after the patient was enrolled into the study must be recorded. Each concomitant drug must be individually assessed against all exclusion criteria/prohibited medication. If in doubt the investigator should contact the Novartis medical monitor before randomizing a patient or allowing a new medication to be started.

Diuretics will be adjusted in all patients to manage the symptoms of heart failure as needed during the study. Changes in diuretic dose must be recorded in the Concomitant Medications eCRF.

Management of comorbidities

The patient should be receiving evidence based medical therapy for relevant comorbidities such as but not limited to HTN, DM, AF, dyslipidemia, COPD and CAD (including diuretics, beta blockers, calcium channel blockers as appropriate). Medical management of comorbidities should be individualized based upon the clinical profile of the patient, taking into consideration age and the number and type of comorbidities.

During the course of the study, investigators should continue to optimize background medications for comorbidities based upon the patient's clinical situation. Elevations in BP during the study should be treated by initiation or adjustment of non RASi therapies. Should the investigator feel that addition of open label RASi or renin inhibitor is required, study drug must be discontinued as outlined above in [section 5.5.5](#) (initiation of open label ACEi should be deferred for 36 hours after discontinuation of study drug). Patients who have discontinued study medication for this reason will continue to be followed within the study and study drug reinitiated as deemed appropriate by the investigator. HbA1c and lipid profile will be performed pre-randomization and during the course of the study; diabetes and lipid management should be optimized during the course of the study as appropriate. All changes in medical therapy for the treatment of comorbidities during the study will be recorded in the eCRF. Additional information will be collected from the investigator for those patients with poorly controlled blood pressure, diabetes and lipids, as to whether medications were adjusted and if not, the reason why no changes in medical therapy were made.

Medications known to raise potassium levels

Potassium-sparing diuretics, potassium supplements, MRAs and any other medications known to raise potassium levels should be used with caution while the patient is receiving the study drug due to the increased possibility of occurrence of hyperkalemia. The investigator is

encouraged to assess patients' potassium levels regularly, especially in those who are receiving these medications.

Phosphodiesterase-5 (PDE-5) inhibitors

PDE-5 inhibitors should be used with caution while the patient is receiving study medication due to the increased possibility of the occurrence of hypotension.

Neseritide

The concomitant administration of LCZ696 with neseritide has not been studied. In the event a study patient requires the concomitant administration of neseritide with the study medications, the investigator should consider starting them at a lower dose or a slower infusion rate while monitoring the patient's BP carefully.

HMG-CoA reductase inhibitors

Caution is recommended when co-administering LCZ696 with atorvastatin or other statins (eg simvastatin, pravastatin) that are substrates of OATP1B1 and OATP1B3 because of the potential to raise plasma statin levels.

5.5.8 Prohibited medication

Use of the treatments displayed in [Table 5-1](#) is **NOT** allowed after the start of study drug due to safety reasons, unless the actions specified are taken.

Table 5-1 Prohibited treatment

Medication	Action to be taken
Any ACEI	Temporarily discontinue study drug while on ACEi. The open label ACEi treatment must be stopped for ≥ 36 hours prior to re-initiation of study drug.
Any ARB	Temporarily discontinue study drug while on ARB. The open label ARB treatment must be stopped prior to re-initiation of study drug.
Any renin inhibitor	Temporarily discontinue study drug while on renin inhibitor. The open label renin inhibitor must be stopped prior to re-initiation of study drug.

ACEIs, ARBs and renin inhibitors

The concomitant use of open-label ACEIs, ARBs or a renin inhibitor is strictly prohibited while the patient is receiving study drug. Should an investigator wish to give open label RASi during the study, study drug will be withdrawn and the patient will continue to be followed within the study. If the patient is to be started on open-label ACEi, study drug must be stopped ≥ 36 hours prior to initiating ACEi treatment. Study drug may be resumed after discontinuation of open label ACEIs, ARBs or a renin inhibitor as described above.

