3.1 Study design

This study is a 24-week, randomized, double-blind, multi-center, parallel group, active controlled study to evaluate LCZ696 compared to individualized medical therapy on NT-proBNP, exercise capacity, symptoms and QoL in patients with HF and preserved left ventricular ejection fraction (LVEF > 40%) (Figure 3-1). Patients will be initially stratified into one of three strata according to prior treatment for comorbidities: ACEi, ARB or no RASi. Patients will then be randomized 1:1 to receive either LCZ or comparator. Patients in the ACEi strata will be randomized to receive either LCZ696 or enalapril. Patients in the ARB strata will be randomized to receive either LCZ696 or valsartan, and patients in the no RASi strata will be randomized to receive either LCZ696 or placebo. Patients in the ACEi and ARB strata must have a history of HTN. There will be no designated proportion of patients in each strata, the strata will populate based upon the patient's prior treatment regimen.

A screening epoch of up to 2 weeks will be used to assess eligibility. Patients on appropriate therapy for comorbidities will be eligible for the study. Patients will be required to have been on stable doses of baseline medications for at least four weeks prior to randomization. After randomization, patients will begin a 1 to 4 week study drug up-titration epoch followed by a 20 to 23 week maintenance epoch (Figure 3-1). Visits to assess safety and efficacy are scheduled at 4 to 6 week intervals during the maintenance epoch. The assessment to address the primary objective of reduction in NT-proBNP will be performed using data up to Week 12, and the primary objective of change in 6MWD and all secondary objectives will be performed using data up to Week 24. No interim analysis (IA) is planned.

[figure not shown]
[figure not shown]

Figure 3-1 Study design

ACEi = angiotensin converting enzyme inhibitor
 ARB = angiotensin receptor blocker
 RASi = renin angiotensin system inhibitors
 * Patients in the ACEi and ARB strata must have a history of HTN

Screening epoch

At screening (Visit 1), patients will sign the informed consent and be assessed for eligibility for study participation through review of study inclusion/exclusion criteria. Patients enrolled in the study will continue their baseline medication regimen and enter a screening epoch of up to 2 weeks in order to allow adequate time for the completion of all qualifying screening and eligibility evaluations.

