Screening NT-proBNP, complete lab evaluations, and pregnancy testing will be assessed by sending samples to the central lab. It may take up to 72 hours to obtain the results of the clinical laboratory assessments to evaluate the patient’s eligibility for the study.

Qualifying echocardiogram (echo) measurements will be based on locally obtained echoes performed within 6 months of Visit 1. If a qualifying echo within 6 months of Visit 1 is not available, the patient must enter the study based on a qualifying echo performed during the screening epoch before any study drug is dispensed to the patient. No imaging method other than echocardiography will be accepted for inclusion into the study.

KCCQ questionnaire will be administered at screening to determine eligibility for study (CSS < 75). A 6MWT will be performed at screening in all patients to familiarize patients with the assessment.

A patient who enters screening but is determined not to be eligible will be considered a screen failure. The investigator may consider re-screening the patient at a later time if he/she believes that the patient's condition has changed and they may potentially be eligible. A patient may be re-screened once. A minimum of 2 weeks must elapse between screen failure and re-screening.

Randomized treatment epoch

At the randomization visit (Visit 101), all patients who fulfill the inclusion/exclusion criteria will be stratified based upon prior therapy as described above. Subsequent to stratification, patients will be randomized into either the LCZ696 or the comparator treatment group at a 1:1 ratio. [Table 3-1](#) categorizes low and high total daily doses for commonly used ACEis and ARBs. Study drug dose levels are outlined in [Table 3-2](#) and study drug up-titration outlined in [Figure 3-2](#). The goal of treatment is to ensure that each patient receives the maximal tolerated dose of study medication.

[figure not shown]
ACEis are required to be discontinued 36 hours prior to the randomization visit (Visit 101) to minimize potential risk of angioedema, and ARBs are required to be discontinued at the randomization visit. With the exception of ACEi, ARB or renin inhibitor, patients will continue on their prior medication for the treatment of comorbidities. All patients must be on stable doses of appropriate therapy for comorbidities for at least 4 weeks prior to enrollment.

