9.4.4 Sensitivity analyses

In order to explore the robustness of the MAR assumption on the primary analysis, a sensitivity analysis will be carried out which assesses the situation where the data are missing not at random (MNAR); In particular, the sensitivity analysis will assume that LCZ696 patients who discontinue due to adverse events, death or lack of efficacy will not have adhered to therapy if they had stayed in the study.

A controlled multiple imputation approach based on pattern mixture models will be applied ([Carpenter and Kenward 2013](#)), whereby all missing data of patients in the LCZ696 group who permanently discontinue study treatment due to: adverse events, death or lack of efficacy, will be assumed to behave like patients in the control group (individualized medical therapy) after permanent discontinuation and will be imputed based on the data from patients in the control group (individualized medical therapy) according to the stratum (defined by prior ACEi/ARB medication usage [ACEi, ARB, None]).

All other missing data will be considered as MAR within each arm and will be imputed using a multiple imputation approach ([Carpenter and Kenward 2013](#)) based on observed data within each arm according to the stratum. Of note, patients who permanently discontinue study treatment, are not considered discontinued from the study. It is planned to continue to collect and use data at scheduled visits even after permanent discontinuation of study treatment.

Furthermore, the missing data patterns in the change from baseline in log(NT-proBNP) and the change from baseline in 6MWD will be explored via by-treatment-group box plots for patients who permanently discontinue from study treatment due to adverse events, death or lack of efficacy, for patients who permanently discontinue from study treatment due to any other reasons, for patients who did not permanently discontinue from study treatment, and for patients who take open label LCZ696 after permanent discontinuation from study treatment.

As additional supportive analyses, the primary analyses for the primary variables (the change from baseline in log[NT-proBNP] at Week 12, and the change from baseline in 6MWD at Week 24) described in [Section 9.4.1](#) will be performed for the following data as applicable:

- Data where the 6MWD after the death were set to missing for patients who died.
- Data where the last observation carry forward (LOCF) approach was performed for missing data.

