- Data where the responses after the first dose of open-label RASi or open-label LCZ696 after permanent discontinuation of the study treatment will be set to missing and considered MAR. (This is called on-treatment analysis.)

The FAS will be used for the above analyses.

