**Table 1-1 Study Medications**

Stratum	Study Medications	
	LCZ696	IMT
ACEi	LCZ696 Active + Enalapril Placebo	LCZ696 Placebo + Enalapril Active
ARB	LCZ696 Active + Valsartan Placebo	LCZ696 Placebo + Valsartan Active
No RASi	LCZ696 Active	LCZ696 Placebo

No interim analysis (IA) for efficacy is planned.

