#### 2.4.2 Prior and concomitant therapies

Prior and concomitant medications will be recorded on the CRF page: “Prior and Concomitant Medications”. Procedures and significant non-drug therapies (prior and concomitant) will be recorded on the CRF page “Surgical and Medical Procedures”.

The missing or partially missing start/end date for prior/concomitant therapies will be imputed based on the Novartis ADaM Governance Board (AGB) global standards.

Prior and concomitant medications/non-drug therapies will be identified based on recorded or imputed start dates and end dates.

Prior medications are defined as any recorded medication with its start date (recorded or imputed) prior to the date of the first dose of the study drug.

Concomitant medications are defined as any recorded medication with its end date (recorded or imputed) later than or equal to the date of the first dose of the study drug AND its start date (recorded or imputed) prior to or equal to the end date of the study.

Prior non-drug therapies are defined as any procedure/significant non-drug therapy with its start date (recorded or imputed) prior to the date of the first dose of the study drug.

Concomitant non-drug therapies are defined as any recorded procedure/significant non-drug therapy with its end date (recorded or imputed) later than or equal to the date of the first dose of the study drug AND its start date (recorded or imputed) prior to or equal to the end date of the study.

For overall and for each stratum (ACEi, ARB, No RASi), prior and concomitant medications will be summarized separately by treatment group, anatomical therapeutic classification (ATC) and PT; prior and concomitant non-drug therapies will be summarized separately by treatment group, SOC, PT.

In addition, for each of the following classes, prior medications and concomitant medications will be summarized by treatment group, for overall and each stratum (ACEi, ARB, No RASi).

- Open label ACEi
- Open label ARB
- Open label ACEi or ARB
- Open label dual RAS blockade
- Open label sacubitril/valsartan
- Renin inhibitors
- Beta blockers
- Diuretics
  - Aldoesterone antagonists
  - Loop diuretics
  - Thiazide diuretics
  - Other diuretics
- Calcium antagonists
- Nitrates
- Other vasodilators
- Cardiac glycosides (digoxin/digitalis glycoside)
- Antiarrhythmic agents
- Aspirin
- Other antiplatelet agents
- Other antithrombotic agents
  - Vitamin-K antagonist
  - NOAKs
- Statins
- Other lipid lowering agents
- Insulins

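### No waiting time is set between ACEi-stratum study drug, which may be enalapril, and open-label sacubitril/valsartan

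*Protocol*

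**What the plan says.** The reason for the 36-hour rule is given in Protocol 3.1: "ACEis are required to be discontinued 36 hours prior to the randomization visit (Visit 101) to minimize potential risk of angioedema". Section 3.6 repeats the requirement. For patients already randomized, 3.6, 5.5.5, 5.5.7 and 5.5.8 require the same wait before an open-label ACE inhibitor is started. The wording in 5.5.8 is: "If the patient is to be started on open-label ACEi, study drug must be stopped ≥ 36 hours prior to initiating ACEi treatment". Section 5.5.5 and the ACEi row of Table 5-1 require it again before study drug is resumed after an open-label ACE inhibitor.

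Table 5-1 has three rows: ACEi, ARB and renin inhibitor. Sacubitril/valsartan is not named. The closest row is the one for ARBs, which says: "Temporarily discontinue study drug while on ARB. The open label ARB treatment must be stopped prior to re-initiation of study drug". It states no number of hours.

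On the blinded drug, Protocol 3.1 says: "Patients in the ACEi strata will be randomized to receive either LCZ696 or enalapril". SAP Table 1-1 shows the comparator arm of that stratum as "LCZ696 Placebo + Enalapril Active".

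Open-label LCZ696 appears in the analysis sections. Protocol 9.4.4 plans box plots "for patients who take open label LCZ696 after permanent discontinuation from study treatment". It also plans a supportive analysis that sets certain values to missing: "Data where the responses after the first dose of open-label RASi or open-label LCZ696 after permanent discontinuation of the study treatment". Protocol 9.5.1.6 and SAP 2.5.4 and 2.6.4 carry the same plans. SAP 2.4.2 tabulates "Open label sacubitril/valsartan" as a medication class of its own.

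**The concern.** Blinding makes ACEi-stratum study drug a potential hazard in two directions. It may be LCZ696, so an open-label ACE inhibitor must not follow too closely. It may also be enalapril, so open-label LCZ696 must not follow too closely. The protocol writes down the first case several times and does not write down the second.

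Section 5.4 limits unblinding before the end of the study to emergencies, so a site cannot normally rule out enalapril. A site that follows the ARB row as written could stop study drug and start sacubitril/valsartan at the next dose time. For a patient on enalapril, that is the sequence for which section 3.1 requires 36 hours. The stake is angioedema, which section 6.5.7 notes can compromise the airway.

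**Working it through.** There is no figure in the plan to reproduce. The check is a comparison of the rules, followed by the dose timing.

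**Step 1. Which sequences have a stated interval?**

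| Sequence | Where covered | Interval |
|---|---|---|
| Prior ACEi, then study drug (may be LCZ696) | 3.1, 3.6 | 36 h |
| Study drug (may be LCZ696), then open-label ACEi | 3.6, 5.5.5, 5.5.7, 5.5.8 | 36 h |
| Open-label ACEi, then study drug (may be LCZ696) | 5.5.5, Table 5-1 | 36 h |
| Study drug (may be enalapril), then open-label LCZ696 | nowhere | none |
| Open-label LCZ696, then study drug (may be enalapril) | nowhere | none |

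Every 36-hour rule names an ACE inhibitor as the non-study drug. The last two rows pair the same two drugs with the roles exchanged. The gap is confined to the ACEi stratum, because study drug in the other two strata contains no ACE inhibitor.

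**Step 2. Does another rule supply the interval?** Reading LCZ696 as an ARB brings in the ARB row, which requires study drug to be stopped but gives no time. Section 5.5.7 requires each new drug to be checked against the exclusion criteria and prohibited list, with the medical monitor contacted in case of doubt. Exclusion 5 in section 4.2 does name LCZ696, but as use within 30 days of Visit 1. Neither route leads to a waiting time after study drug.

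**Step 3. How short could the interval be?** Section 5.5.4 gives dose times of about 08:00 and 19:00. If open-label LCZ696 starts at a scheduled dose time, the interval and the shortfall (36 minus the interval) are:

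| Last study drug dose | Intervals under 36 h | Shortfall | First time at or beyond 36 h | Doses missed |
|---|---|---|---|---|
| 08:00 | 11, 24, 35 h | 25, 12, 1 h | 48 h | 3 |
| 19:00 | 13, 24 h | 23, 12 h | 37 h | 2 |

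**Step 4. How many patients?** The documents give neither the size of the ACEi stratum (section 3.1 fixes no proportion) nor a switch rate, nor the timing of switches. Using assumed values only:

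- An ACEi stratum of 20% to 50% of 2500, randomized 1:1, puts 2500 × 0.20 × 0.5 = 250 to 2500 × 0.50 × 0.5 = 625 patients on enalapril.
- If 0.5% to 2% of them switch: 250 × 0.005 = 1.25 to 625 × 0.02 = 12.5 switchers.
- If 10% to 100% of switchers start within 36 hours: 1.25 × 0.10 = 0.125 to 12.5 × 1.00 = 12.5 patients.

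The hundredfold range reflects the assumptions. It counts early switches, not angioedema events, and it is not an estimate.

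**The case against.** The strongest reply is that LCZ696 is already covered. Section 1.1 describes it as blocking the AT₁ receptor, section 3.4 calls valsartan its ARB component, and section 3.6 tells patients to take no RAS blocker other than study drug. A reader might infer from the gap in Table 5-1 that the protocol lets a patient take study drug and open-label LCZ696 together. The documents do not support that: on a plain reading, simultaneous use is barred. The separate line in SAP 2.4.2 does not undo this, since the classes in that list overlap and include prohibited drugs. This part of the reply stands. It does not supply an interval.

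Second, being listed in an analysis plan does not make a switch permitted or common. The analysis sections mention open-label LCZ696 only after permanent discontinuation, when the drug would be prescribed outside the trial. Section 1.1 gives the approved use as HFrEF, whereas this trial requires LVEF above 40%. That supports a small number. It does not remove the need for a rule, because the hours straight after the last blinded dose are when the interval matters.

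Third, sites know the stratum from the packs (5.5.4), section 5.5.9 expects clinicians to act on the possible assignments, and the 36-hour rule is familiar from randomization. A careful site could work out the wait. The same could be said of open-label ACE inhibitors, for which the protocol still states the wait repeatedly.

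Finally, the Investigator's Brochure, site manuals and product labelling may give the interval. They are not among the documents, so one cannot conclude that sites lack it, only that the protocol does not state it.

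**Conclusion.** The point holds as a single missing interval: between ACEi-stratum study drug, which may be enalapril, and open-label sacubitril/valsartan. The ARB row, followed as written, allows an immediate switch in either direction. The switch out of study drug is foreseen after permanent discontinuation. The return switch is described nowhere, but nothing bars it.

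Two larger inferences should be avoided. One is that a material number of patients is at risk: the documents give no basis for a count, and use is probably rare. The other is that the stop rules need rewriting throughout the protocol: they already reach LCZ696 as an ARB or RAS inhibitor, and only the time is absent.

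It is still worth fixing, because the hazard is one the protocol itself recognizes and the remedy is small. Confidence is medium, since guidance outside the two documents could not be checked.

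**What to change.** Add one row to Table 5-1 for open-label sacubitril/valsartan, with a matching sentence in 5.5.8:

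- Stop study drug while the patient is on it.
- In the ACEi stratum, wait at least 36 hours after the last study drug dose before starting it, including after permanent discontinuation.
- In the ACEi stratum, wait at least 36 hours after its last dose before any re-initiation of study drug.

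A protocol amendment or investigator letter can carry this. Sample size and analyses are unaffected. The downside is two or three missed doses per switch at the scheduled dose times, limited to the ACEi stratum.
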